## PARTNERS HUMAN RESEARCH COMMITTEE

### DETAILED PROTOCOL

from what we would expect by using the model to predict the data. We will also check whether any important predictors have been left out of the model, for example, gender or severity of SCI or level of SCI. These will be tested by including them in revised versions of the model and testing whether the model is substantively improved. It is also important to explore the ‘missingness’ of data. The model we plan to use assumes that missing data are “missing at random.” This can be checked in several ways including comparing the characteristics of observations with and without missing values. More importantly, we can check whether our results would change if the data is “missing not at random” in several ways. For certain outcome variables, it may be the case that subjects who are either at the high end or the low end are more likely to be missing. For example, people at baseline who are very fat or very lean may be more likely to drop out. This can be checked by using constrained multiple imputation where we constrain our imputations to one end of the adiposity range. Comparing the results based on the constrained imputation to the unimputed results gives us a sensitivity analysis.

A second type of sensitivity analysis was originally suggested by Rubin and has been extended by Carpenter, Kenward and White who suggest weighting each imputed result (rather than Rubin’s standard “rules” of averaging the results), where the weight depends on the assumed departure from the MAR assumption. This technique relies on the imputations covering a fairly wide range of values (we would use 100 imputations) but this can be checked and additional data sets imputed if the range is too narrow. Carpenter, *et al.*, provide a graphic method of checking whether the range is wide enough. Finally, if dropouts are much more common than missing an occasion and then returning, we will estimate a pattern-mixture model. However, if there are many people who miss the 3 month measure, but not the 6 month measure, we will not pursue this strategy. A fourth issue deals with the variance structure of the model. Our prime model assumes that the variances are the same across groups. This will be tested by estimating a model with heterogeneous variance structures by group (this is available in some statistical packages, including Stata or SAS).

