### III. SUBJECT SELECTION

We will enroll 60 individuals within twelve months post SCI to obtain data on 50 individuals. One-half of the subjects (N=25) will be randomized to immediately enroll in 6 months of FES-RT. One third (N=18) will be randomized to a wait-list to provide time control data from baseline to 6 months. A wait-list control group is routine in exercise studies because most volunteers are interested in participating in an exercise program. Hence, time controls are difficult to capture since many of those randomized to receive

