## PARTNERS HUMAN RESEARCH COMMITTEE

### DETAILED PROTOCOL

no exercise either drop from the study entirely, or end up pursuing some form of exercise on their own. Therefore, a vehicle for enrollment of a time control group that is acceptable to most volunteers is a wait-list. A six month time control will provide data on expected declines. One-third (N=17) of subjects will be randomized to six months of arms-only-RT. This will provide data on a comparator that represents a form of arms-only exercise that would be available to those with SCI. These subjects will undergo six months of FES-RT after completing arms-only-RT. This will enhance subject retention and provide data for secondary analysis.

To enhance subject recruitment we may enroll subjects into the study before they are 3-months post injury, most likely while they are still in-patients at Spaulding Rehabilitation Hospital. This will help subjects to schedule and plan for transportation for study assessments and training to begin when they reach 3-months post injury. No study assessments will be scheduled before 3-months from time of their SCI. Study participation will not interfere with scheduling of any normal inpatient therapy, nor will study participation take place during normal therapy. In-patients will need to be cleared to participate by their treating physician.

In addition we will enroll another 25 individuals with chronic SCI to serve as a comparator to the acute FES-RT group. Neither a wait-list nor arms-only-RT are required for this population. Time control data from baseline to 6 months are not needed since expected declines would be minimal over this time period after the acute phase of injury. In addition, the fourth aim is solely focused on responses to FES-RT and so a comparator that represents a form of arms-only exercise available to those with SCI is not necessary. Subjects in the chronic group will be at least 1 year post spinal cord injury with adult onset of SCI(SCI occurrence after 18 years of age).

All volunteers will continue with regular physical rehabilitation except for modalities that overlap study interventions (e.g., FES-cycling).

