## VI. BIOSTATISTICAL ANALYSIS

Power analysis: Based on longitudinal exercise capacity data from our lab, extensive sets of power analyses were performed. For the main analysis (acute subjects only), there will be 3 groups of subjects (FES-RT, wait-list and arms-only-RT) and measures at baseline, 3 months, 6 months, except for visceral adiposity (only at baseline and 6 months). The primary analysis (below) will include the three groups and will have as predictors two indicator (dummy) variables for two of the groups, and indicators for the 3 month and 6 month time points and interactions between the time points and the group indicator variables; this will be estimated as a linear mixed model. The only random effect will be for subject. In addition, for the fourth aim, the analysis will only include those entered into FES-RT at the outset, i.e., the FES-RT with acute SCI and all

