## PARTNERS HUMAN RESEARCH COMMITTEE

### DETAILED PROTOCOL

volunteers with chronic SCI. The main analysis will consist of comparisons across time with injury duration as a covariate.

Given logistical constraints, we began with the assumption that data on 50 acute SCI subjects (out of 60 recruited - a ~15% dropout rate) would be advantageous if that sample size allowed us to find differences that are substantively meaningful. This group would be allocated (randomly; see below) as 40% to FES-RT and 30% to each of wait-list and arms-only-RT. We also checked other total sample sizes and allocation rules (e.g., data from 20 in each group, data from 25 in FES and 15 in each of the other two groups). In addition, 25 individuals with chronic SCI would provide sufficient power to detect meaningful (e.g., >15%) differences between acute and chronic SCI at the same power outlined below.

These calculations were performed assuming an alpha of 0.05 and a correlation between baseline and 6 month measure of about 0.7; unless the correlation was very different from 0.7 (e.g., 0.25), there was little difference in the results. This shows that we will have sufficient power under this plan with a sample size of 50 acute SCI subjects and allocation of 20/15/15. Subjects will be randomized at the ratio of 1.33:1:1 to each of the three groups by a randomization plan constructed by the project statistician. The investigator will have no knowledge of group assignment until the time of subject enrollment. During the study, there can be no blinding of the subject or the investigator, however all measures will be obtained by an individual blind to subject group assignment.

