*Primary data analysis:* The primary analysis will test whether the FES-RT has 'better' values of the outcome variables at 6 months post-baseline. A general linear mixed model with a random effect for subjects will be used to conduct an intent-to-treat analysis. The main predictors will be indicator variables for group with the FES-RT group as the reference group and indicators for each of the other two groups, the time at which the outcomes were measured and treatment group by time interactions; menstrual status (with men coded the same as women who are not menstruating) will be included as a dummy variable; for the insulin resistance measure, body weight/fat changes will be included as a predictor. In a secondary analysis, we will include interactions terms between the group indicators and the 3 month indicator. In addition, similar models to the above will be estimated for secondary outcomes.

*Checking and Sensitivity Analyses:* It is important to ensure that data idiosyncrasies do not impact the results and that the results are generalizable. We will check for systematic differences between the model and the data using graphs, such as comparisons of predicted and observed values of the outcome variable, and other standard diagnostics. An extension of this idea is to simulate new sets of data based on our model and use the simulated data as a reference test group by comparing this to the observed data; we do this to look for situations in which the data appear different

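### The primary model for Aims 1-3 omits time since injury, which the plan itself treats as prognostic; the cost is precision and chance imbalance, not bias.

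*Combined protocol and SAP*

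**What the plan says.** **Primary model.** Section VI, Primary data analysis: "The main predictors will be indicator variables for group with the FES-RT group as the reference group", together with time and group-by-time terms. It adds that "menstrual status (with men coded the same as women who are not menstruating) will be included as a dummy variable", and the insulin resistance model also takes change in body weight or fat. The power paragraph says "The only random effect will be for subject". Time since injury is not among these terms, and the randomisation text names no stratification factor.

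**Model checks.** Checking and Sensitivity Analyses asks whether "any important predictors have been left out of the model, for example, gender or severity of SCI or level of SCI". The rule is: "These will be tested by including them in revised versions of the model and testing whether the model is substantively improved". No threshold follows, nor any statement of which model is then reported. Time since injury is not among the examples.

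**Entry window.** Section III: "We will enroll 60 individuals within twelve months post SCI". It also bars any assessment before month 3.

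**Injury duration elsewhere.**
- Section I places the marked loss of function in the first year.
- Section II, Aim 4, hypothesises that declines in all variables, and the size of adaptation, are related to injury duration.
- Section III gives the chronic group (at least 1 year after injury) no time control because "expected declines would be minimal over this time period after the acute phase of injury".
- Section VI analyses Aim 4 by "comparisons across time with injury duration as a covariate", and that analysis includes the acute FES-RT subjects who also serve Aims 1-3.

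**The concern.** The wait-list arm is there to show how much acute subjects decline without row training. On the plan's own account that decline belongs to the first year. A subject who enters at month 3 is followed wholly inside that year; one who enters at month 12 is followed wholly outside it. Expected decline therefore plausibly varies with entry time, but the model fits one time course per arm.

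The variation in decline goes into residual error, and any chance difference in entry time between arms of 20 and 15 passes into the 6-month contrast. Neither design nor analysis deals with it. Separately, because the plan does not say what follows when a revised model fits better, the choice of reported model could come to depend on the data.

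**Working it through.** **Inputs from the documents.** 20/15/15 subjects with data and a baseline to 6-month correlation of about 0.7 (Section VI, Power analysis); assessment from month 3, entry to month 12 (Section III); six months of follow-up. Section III also gives other arm numbers; those of the power paragraph are used here.

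**Assumptions.** Entry is uniform over months 3-12. Six-month decline falls linearly from D baseline SDs for entry at month 3 to zero for entry at month 12, with D = 0.5, 1.0 or 1.5. The plan gives no SD, effect size or expected decline.

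**1. The plan's own figures.** Enrolment: 50/(1 - 0.15) = 58.8, so 59 against the stated 60. Allocation: 50 x 1.33/3.33 = 20 and 50 x 1/3.33 = 15. Both agree. No numeric power is stated, so none can be reproduced.

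**2. Follow-up windows.** Earliest: 3 + 6 = month 9. Latest: 12 + 6 = month 18. Anyone who enters after month 6 is followed past the first year; under uniform entry that is (12 - 6)/(12 - 3) = 67% of subjects.

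**3. Chance imbalance, 20 vs 15.** The SD of entry time is 9/√12 = 2.60 months. The SD of the arm difference in means is 2.60 x √(1/20 + 1/15) = 0.89 months. By simulation the difference exceeds 1 month in 26% of randomisations and 2 months in 2.4%. If duration acts alike in both arms, this contributes (D/9) x 0.89 = 0.05, 0.10 or 0.15 SD of chance error to the contrast. That error is already part of the unadjusted standard error, √[(0.6 + D²/12)(1/20 + 1/15)] = 0.27, 0.28 or 0.30 SD, where 0.6 = 2(1 - 0.7). It is not a second loss.

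**4. Main effect or interaction.** In a simulated mixed model with complete data, adding duration as a main effect only changed the 6-month group-by-time estimate by less than 1e-14. Only a duration-by-time term acts on the contrast.

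**5. Net gain if duration acts alike in all arms.** Variance ratio, unadjusted to adjusted = [(0.6 + D²/12)/0.6] / [1 + 1/(50 - 3 - 2)]. The divisor, 1.022, is approximately the cost of estimating one slope.

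| D (SD) | Ratio | Net change in precision |
|---|---|---|
| 0 | 1/1.022 = 0.98 | -2% |
| 0.5 | (0.621/0.6)/1.022 = 1.01 | +1% |
| 1.0 | (0.683/0.6)/1.022 = 1.11 | +11% |
| 1.5 | (0.788/0.6)/1.022 = 1.28 | +28% |

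Simulation agrees: about 1%, 10% and 20-30%.

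**6. Net gain if FES-RT abolishes decline.** A common slope then fits no arm well. Simulation gives about -2%, +1% and +6%. Hand check at D = 1.5 (D²/12 = 0.1875), with both comparators declining: the pooled slope is 30/50 = 0.6 of theirs. Unadjusted variance is 0.6/20 + 0.7875/15 = 0.0825. Adjusted variance is [(0.6 + 0.36 x 0.1875)/20 + (0.6 + 0.16 x 0.1875)/15] x 1.022 = 0.0770. The ratio is 1.07, within about a point of the simulation.

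**7. The open model check.** With three irrelevant binary covariates, 20 vs 15 and nominal 5%, simulated type I error is 5.0% with none and 4.9% with all fixed in advance. It is 5.7% if covariates are kept at p < 0.10, and 7.1% if the best of the eight models is chosen by the treatment p-value.

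**The case against.** The strongest case is that adjustment may buy almost nothing. The trial expects FES-RT to prevent decline. If so, entry time matters only in the comparators, and a common duration term gains between -2% and +6%. Inpatient recruitment may also cluster entry near month 3, which would narrow the spread and shrink any gain. Both points stand as limits on size. They are not the only reading, however. Aim 4 expects adaptation to grow with injury duration, which implies a slope in the FES-RT arm in the same direction as in the comparators: later entrants fare better in both.

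Several stronger readings are tempting, and the documents do not support them.
- A reader might infer that the plan says decline fades before the entry window closes. It does not. The remark about minimal decline concerns chronic subjects, and the acute window ends where theirs begins. Only the passage of late entrants' follow-up beyond month 12 can be deduced.
- A reader might infer that covariates for the primary model are chosen by fit. The primary predictors are listed, and the test of further ones sits under sensitivity analyses. What is missing is a sentence that rules out replacement. The example list is open, so time since injury is not excluded from it. Outcome assessors are to be blind to group.
- A reader might want sex, level and severity added as main effects. With complete data, terms constant within subject leave the 6-month contrast essentially unchanged, so nothing here calls for that.

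**Conclusion.** The point holds as a matter of efficiency. The primary model and the stated randomisation both ignore a variable that the plan calls prognostic and uses in Aim 4. Because allocation is random, the unadjusted comparison remains valid: the loss is precision, including exposure to chance imbalance in small arms, not systematic bias.

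The size is uncertain. Over D = 0.5 to 1.5 SD, the gain from adjustment runs from about 1% to 20-30% if duration acts equally in all arms, and from about -2% to +6% if FES-RT abolishes decline. If duration is unrelated to change, about 2% is lost. These figures rest on uniform entry, linear fading, the plan's correlation of 0.7 and arms of 20/15/15; D and the entry pattern are assumptions. A small, bounded cost against a possibly useful gain favours adjustment. The open model check is a lesser matter: selection by fit alone inflates type I error little, and one sentence closes the gap.

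**What to change.** In Section VI, Primary data analysis, add baseline time since injury and its interactions with the 3- and 6-month indicators. For visceral adiposity, which is measured only at baseline and 6 months, only the 6-month interaction applies. State the functional form (for example, linear in months) and define the anchor date in the same way for every arm. A main effect alone is not enough.

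In Checking and Sensitivity Analyses, state that revised models are sensitivity analyses and cannot replace the primary model, whatever their fit.

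The cost is SAP wording and about one degree of freedom per follow-up time, or some 2% of precision if duration proves irrelevant. No new data are needed: injury date already governs eligibility and serves Aim 4.

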## PARTNERS HUMAN RESEARCH COMMITTEE

### DETAILED PROTOCOL

#### **VII. RISKS AND DISCOMFORTS**

Moderate risks are associated with exercise testing and exercise training. Some discomfort and feeling of fatigue will be experienced during these tests. There are other risks associated with these tests including abnormal blood pressure responses, fainting, irregular, fast or slow heart rhythm, and in rare instances, heart attack, stroke, or death. Wearing the mouthpiece during the VO2max testing may cause feelings of claustrophobia. Exercise training may induce some muscle or joint discomfort when beginning an exercise program and could result in tendonitis and/or musculoskeletal overuse injuries over time. The electrical stimulation unit can cause tingling, pins and needles sensations on the skin, skin irritation, increased muscle spasticity and autonomic dysreflexia (signs include: headache, nausea, rise in blood pressure, sweating, and goosebumps). There is some discomfort with venipuncture and the lancet used on the finger for lactate measurement and there is the possibility of swelling and bruising at the site(s), there is also a slight chance that individuals become dizzy and even faint. The neck suction/pressure collar may cause some discomfort and a mild choking feeling which resolves quickly when pressure or suction is turned off.

The risk of DXA scanning is minimal. Participants in this study will be exposed to radiation from two or three DXA scans of the whole body depending on study group. The total amount of radiation that will be received from participation in this study is equal to a whole body exposure of less than 0.26 milliSieverts (mSv). For comparison, the average person in the United States receives a radiation exposure of 3.6 mSv per year from natural background sources (the earth and the sky). The dose from participation in this research study is about the same as what a person would normally receive in less than one month from these natural sources. Scientists disagree on whether radiation doses at these low levels are harmful. A possible effect that could occur at doses associated with this study is a slight increase in the risk of developing cancer later in life. Women of childbearing potential will be given a urine or serum pregnancy test before any DXA scan and not scanned if they are pregnant.

There are no known risks associated with the EKG or the echocardiogram. A subject must remove his or her shirt and have sticky patches applied to the chest for the electrocardiogram (EKG) and have gel applied for the echocardiogram. In some cases, chest hair may have to be shaved where the EKG patches are placed. If a structural abnormality is identified on an EKG or echo, the subject would be given this information and referred to his or her own doctor for further evaluation. Subjects may feel lightheaded or short of breath during the pulmonary function tests, there is also a slight chance that individuals become dizzy and even faint.

## PARTNERS HUMAN RESEARCH COMMITTEE

### DETAILED PROTOCOL

#### **VIII. POTENTIAL BENEFITS**

Volunteers will have the opportunity to participate in a supervised exercise program, which may improve their overall cardiovascular fitness and endurance during activities of daily living as well as decrease risk of chronic disease.

#### **IX. MONITORING AND QUALITY ASSURANCE**

The program director will be responsible for monitoring the completeness of all data and source documents. The Principal Investigator will monitor the informed consent procedures in accordance with the Informed Consent Compliance Checklist of Partners HealthCare Systems HRQIP. The subjects data/protocol adherence will be monitored by the research coordinator at each step in the study including. Checklists and note pages are used to note any deviations or omissions from the protocols. All spinal cord injured participants will be asked the “Pre-Study Screening” questions before every visit. The Cardiovascular Research Laboratory Medical Emergency Safety Plan will be followed in the case of an adverse medical event. Any clinical/health related issues would be immediately presented to the subject (i.e. abnormal EKG, blood chemistries, etc) to determine appropriate notification (ie. current physician or appropriate specialist) Based on the seriousness of the situation [name] may be contacted to provide clinical guidance on the appropriate course of action.

Serious adverse events will be reported to the IRB via phone, email, or fax. The principal investigator will follow this with a full written report using the PHRC Adverse Event Form within 10 working days. If a mild or moderate adverse event occurs that is definitely, probably, or possibly related to the study, a written report will be sent to the IRB within 20 working days. All other events will be summarized in a progress report at continuing review.

